This study will employ a 2-arm randomised controlled trial, including 1 symptom monitoring intervention group and 1 non-monitoring control group. The main analysis will be a 2 by 2 mixed between/ within-subjects ANOVA. The between-subjects component will compare symptom differences between the symptom monitoring intervention group and the usual care control group. The within-subjects component will compare symptom changes between baseline and after 2-weeks of daily symptom monitoring, and between baseline and after an interval of 2 weeks without monitoring, in the control group. The interaction will establish whether symptom changes differ over time according to whether women are in the symptom monitoring or control group. It is expected that improvements in well-being will occur over time in the symptom monitoring group, in comparison to the control group e.g., positive reactions will increase from baseline, whereas negative reactions will decrease. Symptom reports will be collected using the DRK (Boivin & Takefman, 1995). The intervention group will record their symptoms at baseline and every day for 2-weeks (although only baseline to follow up changes will be subject to analysis), the control group will record their symptoms at baseline and after an interval of 2-weeks with no daily monitoring. The DRK has been used previously in randomised trials of women's reproductive health (e.g., Boivin & Takefman, 1995; Ockhuijsen et al., 2014) to establish the effects of symptom monitoring. This research will take place electronically, questionnaires will be presented to participants in the form of JISC Online Surveys and accompanying information will be attached to emails as Word documents. This study has been designed in this way in response to the ongoing 2020 COVID-19 pandemic. The study admin will be managed by [name] via a dedicated USW email address: [contact].

Research design figure:

All participants:

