10. PARTICIPANTS

Discuss the number of participants required, from where the participants will be recruited, and the exclusion and inclusion criteria. Please include power calculations where applicable.

Participants will be recruited using a research poster which will be presented both on JISC's research participant finder service: www.callforparticipants.com and social media sites: Facebook, Instagram and Twitter. **See Appendix 7 to view the recruitment poster as presented on www.callforparticipants.com, and shared on social media sites.** All participants who meet eligibility criteria and research terms will be provided with a £20 Amazon voucher after completing the study to thank them for their time.

Participants will be randomised using online resource: www.randomizer.org. Randomizer is a free resource for researchers in need of a quick way to generate random numbers or assign participants to experimental conditions. This site can be used for a variety of purposes, including psychology experiments, medical trials, and survey research. Randomizer works by generating a series of random unique numbers, therefore to allocate participants into the intervention group 1 set of 39 random numbers were generated using values ranging from 1-78. These figures were chosen following insights from the power analysis (see below).

Random number generation will be used to allocate participants into groups. Participants will be assigned a number when they join the study by submitting the baseline survey- this number will reflect the order in which they joined the study i.e. the first person to join will be assigned as number 1, the second will be assigned as number 2. This number will determine whether they are in the control or intervention group by using random numbers generated by randomizer.com. Randomizer works by generating a series of random unique numbers, therefore, to allocate participants into the intervention group, 1 set of 39 random numbers will be generated using values ranging from 1-78. If the participant's assigned number matches one of the 39 random numbers generated, they will be allocated into the intervention group. If their number is not on the random number list, they will be allocated into the control group.

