Inclusion criteria: this study will involve adult females, who report at least 2 hot flushes per day, with self-reported peri- or post-menopausal status. Women taking menopause-specific treatments (e.g. HRT or anti-depressants) are included in this study provided they reach the criteria for hot flushes and are otherwise healthy.

Exclusion criteria: participants will be screened out of the survey if they answer no to the following questions, which will be presented before the information sheet, consent form and main survey: "Are you over the age of 18?", "Are you experiencing at least 2 hot flushes per day?", and "Are you experiencing either perimenopause or menopause?"

Additionally, care will be taken to identify and exclude outliers from analyses, especially when considering the data of those who say they have been diagnosed with chronic or severe conditions with symptoms overlapping with menopausal symptoms, including chronic fatigue syndrome, fibromyalgia, cancer, heart

**FACULTY OF LIFE SCIENCES AND EDUCATION
FACULTY ETHICS SUB GROUP APPLICATION FORM**

disease, thyroid disorders, depression and other mental illnesses. As the research team is not medically trained, we are not able to ascertain definitively if women do have any medical conditions. However, women will be informed in the information sheet that they should not participate if they have these conditions for the reason stated above, and those who report such conditions in the demographic and medical history will be statistically assessed with caution using univariate and multivariate analyses, and data from these individuals will be excluded where necessary. Participants who do not complete all study materials or comply fully with the experimental protocol will also be excluded from analyses. Participants who report demographic characteristics that have been related to poorer health will also be assessed as covariates. Differences in symptoms between groups according to employment status, living status and relationship status will be analysed to understand variances in health between these groups. This is because unemployed, or single, or individuals who live alone are more likely to report poorer health than others.

Power analysis:

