22. DATA ANALYSIS / STATISTICS

Please describe the arrangements for analysing your data (qualitative and quantitative). Where appropriate discuss what data/statistical analysis will be completed. Where used, please remember to discuss sample size and how the sample size was decided upon.

2 x 2 mixed between-within ANOVA:

The main analysis will include a 2x2 mixed between-within ANOVA to assess differences in symptoms among the symptom monitoring and control groups before and after the 2-week research period. The between-subjects component will encompass the differences in symptoms between the control and intervention groups; the within-subjects variable refers to differences in symptoms before and after the 2-week study period. It is expected that after 2 weeks of symptom monitoring the intervention group will exhibit a greater reduction in symptoms in comparison to the control group (i.e., a significant group x time interaction). As discussed, a power analysis was calculated to identify the minimum sample size needed to detect moderate effects, resulting in the decision to recruit 78 participants, with 39 participants being randomised into each group.

Regressions:

Multiple regressions will explore whether help-seeking intentions as continuous variables as predicted by symptom monitoring group (dummy coded), self-efficacy in patient-doctor communication, self-efficacy in shared decision making, health and symptom awareness, and self-efficacy in goal orientated behaviour, health anxiety, and menopausal symptom changes.

Logistic regressions will establish whether control or intervention group membership (as measured as a dichotomous “Invention/Control” variable) is predicted by health anxiety, variances in emotions and symptoms, help-seeking intentions, self-efficacy in patient-doctor communication, self-efficacy in shared decision making, health and symptom awareness, and self-efficacy in goal orientated behaviour.

Correlations:

FACULTY OF LIFE SCIENCES AND EDUCATION
FACULTY ETHICS SUB GROUP APPLICATION FORM

Correlations will also be computed to assess for associations between certain variables. For example, higher neuroticism X higher negative emotions.

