27. PAYMENT TO RESEARCH PARTICIPANTS

Please note, participants should not be paid for taking risks. Payment should not be set to a level that would unduly influence potential participants. Information pertaining to participant payment should be included on the Participant Information Sheet.

Will participants be paid? YES

If yes, please give details.

All 78 participants will receive a £20 Amazon gift voucher. The £20 Amazon voucher will be emailed to respondents at the end of the 2-week research period pending they fully adhere to the instructions provided and do not withdraw. To adhere to the research instructions, all participants must fully complete the baseline and follow-up measures, and intervention participants must complete the DRK monitoring form each day for 14 days within 24 hours of receiving the links via email. All participants must complete the follow-up survey within 24 hours of receiving the link via email. This information will be provided on the information sheet, and the consent form will include items which will obtain confirmation that participants are aware that they must complete the requirements of the study in order to claim their Amazon voucher.

Some participants allocated into the control group may feel they would like to try the symptom monitoring intervention themselves. While it would be impractical to offer the exact intervention to control participants after the research period, a list of online symptom monitoring tools and mobile apps (e.g., Health and Her's online symptom tool, Clue's mobile app for period tracking) will be provided on the final debrief sheet which will be provided after the follow-up questionnaire is completed (**see Appendix 12, page 9 to view the follow-up debrief sheet, see this link: <https://southwales.onlinesurveys.ac.uk/follow-up-questionnaire-preview> to the follow-up survey which also presents the debrief sheet**).

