Appendix 5: Templates of the text message reminders and daily DRK email reminders

Appendix 5: Templates of the daily DRK email reminders and text message reminders

Daily DRK email reminder template:

Hi,

Welcome to Day 2 of the monitoring study.

Your username is: **pilot1**

Please remember this username as it will be used to provide you with your £20 voucher, you can

contact [contact] if you forget it.

You may open the **Day 2 survey** in your web browser by clicking the link below:

<https://southwales.onlinesurveys.ac.uk/daily-record-keeping-form-pilot-copy>

If the link above does not work, try copying this link into your web browser:

<https://southwales.onlinesurveys.ac.uk/daily-record-keeping-form-pilot-copy>

This link is unique to you and should not be forwarded to others.

To claim your £20 Amazon voucher, **you must complete all 14 of the 5-minute surveys within 24 hours of receiving the links via email, and you must complete the final follow-up survey within 24 hours of receiving the link via email.**

Please do not reply to this email. If you would like to withdraw your data, please

email [contact]. You can also email [contact] if you would like to opt out of receiving text message reminders.

If you have any questions or concerns about this study, please email: [REDACTED]

We thank you again for your participation,
The Research Team

**FACULTY OF LIFE SCIENCES AND EDUCATION
FACULTY ETHICS SUB GROUP APPLICATION FORM**

Daily text message reminder template:

Today's survey has been sent to the email address you have provided. You can complete this survey now via this link: <https://southwales.onlinesurveys.ac.uk/daily-record-keeping-form-pilot-copy>. Please make sure you complete and return this survey by 10am tomorrow morning to be eligible for the voucher. We thank you for your participation in this research. To opt out of text message reminders please email: [contact]

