To be eligible for the £20 Amazon voucher, you must complete the follow-up survey within 24 hours of receiving the link via email.

Please do not reply to this email. If you would like to withdraw your data, please

email [contact]. You can also email [contact] if you would like to opt out of receiving text message reminders. If you have any questions or concerns about this study, please email: [REDACTED]

We thank you again for your participation,

The Research Team

The follow-up email template sent to participants after 14 days of either usual care or completing daily DRK surveys:

Hi,

You have now reached the end of the study; all you need to do now is complete the final follow-up survey (see the link below).

Your username is: **pilot1**

Please remember this username as it will be used to provide you with your £20 voucher, you can contact [contact] if you forget it.

You may open the **follow-up survey** in your web browser by clicking the link below:

**FACULTY OF LIFE SCIENCES AND EDUCATION
FACULTY ETHICS SUB GROUP APPLICATION FORM**

<https://southwales.onlinesurveys.ac.uk/follow-up-questionnaire-preview>

If the link above does not work, try copying this link into your web browser: <https://southwales.onlinesurveys.ac.uk/follow-up-questionnaire-preview>

This link is unique to you and should not be forwarded to others.

Once you have completed the follow-up survey you will be sent your **£20 Amazon gift voucher via email**, provided you have completed all surveys within the allocated time frames and have met the terms and conditions (see the information sheet attached for more information).

To be eligible for your £20 Amazon voucher, **you must complete the follow-up survey within 24 hours of receiving it**.

Please do not reply to this email. If you would like to withdraw your data, please email [contact]. You can also email [contact] if you would like to opt out of receiving text message reminders.

If you have any questions or concerns about this study, please email [REDACTED]

We thank you again for your participation,

The Research Team

**FACULTY OF LIFE SCIENCES AND EDUCATION
FACULTY ETHICS SUB GROUP APPLICATION FORM**

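### Women who miss any study form are excluded after allocation; 14 of those forms exist in the monitoring arm only, and the available text gives no as-randomised analysis

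*Combined protocol and SAP*

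**What the plan says.** Section 10 (exclusion criteria) sets the rule: "Participants who do not complete all study materials or comply fully with the experimental protocol will also be excluded from analyses". The same section fixes when allocation happens: "Participants will be assigned a number when they join the study by submitting the baseline survey", and that number determines the arm.

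Full compliance is not defined in section 10. The nearest definition is in the payment terms of section 27: "intervention participants must complete the DRK monitoring form each day for 14 days within 24 hours of receiving the links via email", and for both arms, "All participants must complete the follow-up survey within 24 hours of receiving the link via email". The daily reminder in Appendix 5 repeats the first condition: "you must complete all 14 of the 5-minute surveys within 24 hours of receiving the links via email". Section 8 confirms that controls complete measures only at baseline and on day 15.

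On the analysis, section 8 says of the daily forms "although only baseline to follow up changes will be subject to analysis". Section 22 says: "The main analysis will include a 2x2 mixed between-within ANOVA to assess differences in symptoms among the symptom monitoring and control groups". It names no analysis set and no method for missing data. Section 14 keeps the data that drop-outs have already submitted unless they withdraw them, but does not say those data are analysed.

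Section 10 also allows outliers to be removed, and women reporting certain overlapping conditions to be excluded as needed after statistical checks, although such women are told not to take part. It gives no threshold, timing or blinding rule for either.

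**The concern.** Randomisation makes the arms comparable at allocation. An exclusion that depends on later behaviour can undo this, most plainly when the behaviour is demanded of one arm only. Here a monitoring woman who skips one daily form is dropped, while a control in the same circumstances has no such form to skip.

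Section 8 itself does not use the daily forms in the main comparison. A woman who missed one day but returned follow-up has both measurements that the main analysis needs, yet is discarded. If women who keep completing forms differ in symptom change from those who do not, the group-by-time interaction mixes the effect of monitoring with selection of the women who kept going. The first hypothesis rests on that interaction, and recruiting more women would not remove the bias.

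**Working it through.** **1. The plan's own allowance.** Section 10 (power analysis) requires 52 women and cites 33% attrition: 52 / (1 − 0.33) = 77.6, rounded up to 78. This reproduces. The allowance is 78 − 52 = 26 women, and 26/78 = 33%. It is not split by arm or by reason for loss. It protects numbers, not comparability.

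**2. Forms after allocation.** Monitoring: 14 DRKs + 1 follow-up = 15. Control: 1 follow-up. Difference: 14. The imbalance does not depend on the time limits, because a requirement to complete all materials already catches a missed DRK in one arm only. If the payment terms define compliance, a late DRK counts too.

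**3. Two groups of women to keep apart.**
- (i) Women who return follow-up but miss, or are late with, a DRK. The rule discards them; an as-randomised analysis restores them.
- (ii) Women with no follow-up. Their outcome is missing under any rule.

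**4. How large group (i) could be (assumptions only).** Suppose 90% in each arm return follow-up, days are independent, and every woman has the same daily completion rate q. Controls kept: 39 × 0.90 = 35.1. Monitoring women kept: 39 × 0.90 × q^14.

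| q | q^14 | Monitoring kept | Group (i): 35.1 − kept |
|---|---|---|---|
| 0.99 | 0.869 | 30.5 | 4.6 |
| 0.98 | 0.754 | 26.5 | 8.6 |
| 0.97 | 0.653 | 22.9 | 12.2 |
| 0.95 | 0.488 | 17.1 | 18.0 |

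At q = 0.98 retention is 26.5/39 = 68% against 90%. If missed days cluster in a few women, fewer are lost at the same average rate. This table measures loss only; with identical rates for all women there would be no bias.

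**5. Bias if completing is related to change (assumptions only).** Let ρ be the correlation between completing and improving, equal in both arms, and let p be the proportion kept. The spurious difference in SDs of change is ρ × [φ(z_M)/p_M − φ(z_C)/p_C], with z = Φ⁻¹(p). For p_M = 0.67 and p_C = 0.90, about 17 women are lost (39 × 0.33 + 39 × 0.10 = 16.8), and the bracket is 0.5405 − 0.1950 = 0.3455.
- ρ = 0: no difference
- ρ = 0.2: 0.069
- ρ = 0.5: 0.173
- ρ = −0.3: −0.104

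Simulated two-sided type I error (39 per arm randomised, 200,000 trials, t test on change, which is the 2×2 interaction test): 5.0%, 5.8%, 10.5% and 6.9% in the same order. At ρ = 0.3 it is 6.8%. With 67% kept in both arms it stays at about 5% for every ρ tried.

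**The case against.** The strongest reply is that the allowance of 26 is for attrition, not for this rule. That stands. A reader might infer that the rule causes all 26 losses and that they fall mostly on monitoring. With 90% of controls kept, monitoring retention would be (52 − 35.1)/39 = 43%, and ρ = 0.5 would give 0.36 SD and a type I error of 23.6%. The documents do not support that split, and many of those losses could be women with no follow-up. For such women a mixed model would not rescue the comparison: in that scenario, with assumed baseline–follow-up correlations of 0.3 to 0.7, it still leaves about 0.25 to 0.31 SD. Changing the analysis set repairs group (i), not group (ii).

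Second, full compliance is inferred partly from payment terms, and the information sheet is not in the available text. The time limits are therefore only an apparent part of the rule. The missed-form imbalance does not depend on them.

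Third, section 8 words the day-15 request in the monitoring arm as following the return of all 14 DRKs. If that were a condition, partial adherers would have no follow-up and group (i) would nearly vanish. The heading in Appendix 6, "The follow-up email template sent to participants after 14 days of either usual care or completing daily DRK surveys", can be read either way. But section 8 (all participants), section 9, section 15 and Appendix 13 all indicate that follow-up goes to both groups or to every participant, so it would be too strong to say that follow-up is withheld.

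Fourth, excluding women for conditions reported at baseline, by a rule blind to arm, would not break randomisation. That stands; the fault there is the open discretion.

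**Conclusion.** The concern holds. As written, the plan excludes women after allocation by a criterion with 14 more ways to fail in one arm. It does so needlessly for women who return follow-up, and no as-randomised analysis appears in the available text. This should be corrected before any data are analysed.

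The size is unknown. The 0.07 to 0.17 SD range rests on an assumed retention split and an assumed correlation. It measures the rule's own effect only so far as the extra monitoring losses are in group (i). A reader might also infer that the bias must favour monitoring; the documents give no basis for a direction. The loose provisions for outliers and listed conditions are a secondary matter: they let the analysis set be chosen after outcomes and allocation are seen.

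**What to change.** 1. **Analysis set.** Replace the section 10 sentence with: *The primary analysis includes all randomised women in their allocated arm, except those who withdraw their data, whatever number of DRKs they returned and whether or not forms were on time. The full-compliance set is reported only as a labelled sensitivity analysis. Follow-up return is reported by arm.*
2. **One primary analysis.** In sections 8 and 22, replace the 2×2 ANOVA as the main analysis with a mixed model for the group-by-time effect, using all available baseline and follow-up data. It tests the same interaction. Replace rather than add, so that only one primary analysis is named.
3. **Missing follow-up.** Add a delta-adjusted sensitivity analysis with a range fixed before data are seen, for example 0 to 0.5 SD of change, in either direction and by arm.
4. **Follow-up for all.** State in section 8 (intervention group) that the day-15 survey goes to every randomised woman however many DRKs she returned.
5. **Secondary.** Write the outlier and listed-condition rules in advance, apply them blind to arm and outcome, and report results with and without these removals. The DRK deadline is the end of the day in section 8 but 24 hours, or 10am next morning, in section 27 and Appendix 5. These should be reconciled, though this is peripheral once timing no longer decides inclusion.

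**Cost.** Wording in sections 8, 10 and 22, and possibly section 27 or Appendix 5. Every randomised woman already has a baseline DRK. If section 8 was meant to make follow-up conditional, item 4 adds some follow-up surveys through the existing emails. Partial adherers may dilute the estimate slightly. Because a missed DRK forfeits the voucher, follow-up may still be missing more often in the monitoring arm, which is why return by arm and item 3 are needed.
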